Using a 2x2 factorial design (Table 1), young adults who smoke CCs and use ECs will be randomly assigned to one of four conditions: A) NRT plus text messages to quit CCs only, B) NRT plus text messages to quit CCs and ECs simultaneously, C) text messages alone to quit CCs only, or D) text messages alone to quit CCs and ECs simultaneously. We will recruit, consent, and randomize 390 participants with the aim of retaining 312 (80%) by the end of treatment. Participants in each condition will complete a survey at baseline, weekly surveys throughout the 3-month treatment period, brief daily surveys for one week before and one week after the assigned quit date, an end of treatment survey, and a survey at a follow-up 6 months after treatment began (Figure 1). In addition, participants will be encouraged but not required to submit breath CO samples at baseline, all weekly surveys, the end of treatment, and the 6-month follow-up using the CoVita iCO personal smokerlyzer (<https://www.covita.net/ico-overview/>).

Table 1. 2x2 factorial design

Nicotine replacement therapy (NRT)	Text-messages to quit CCs only vs quit CCs & ECs	
	Quit CCs & continue ECs	Quit CCs & quit ECs
Yes	A) NRT & text messages to quit CCs & continue ECs	B) NRT & text messages to quit CCs & quit ECs
	C) Text messages alone to quit CCs & continue ECs	D) Text messages alone to quit CCs & quit ECs

[figure not shown]

Figure 1. Timeline of study procedures. CC=Combustible cigarettes; EC=Electronic cigarette; NRT=Nicotine replacement therapy.

Procedures: Describe all procedures (sequentially) to which human participants will be subjected. Identify all procedures that are considered experimental and/or procedures performed exclusively for research purposes. Describe the types, frequency and duration of tests, study visits, interviews, questionnaires, etc.

Note: A clinical research protocol may involve interventions that are strictly experimental or it may involve some aspect of research (e.g., randomization among standard treatments for collection and analysis of routine clinical data for research purposes). It is important for this section to distinguish between interventions that are experimental and/or carried out for research purposes versus those procedures that are considered standard therapy. In addition, routine procedures performed solely for research purposes (e.g., additional diagnostic/follow-up tests) should be identified.

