Statistical methods. Baseline participant characteristics, including socio-demographic information and tobacco use history, will be compared between the four conditions using analyses of variance for continuous and chi-square tests for categorical variables. Differences between conditions at baseline will be considered as potential covariates in subsequent analyses. Consistent with the intent-to-treat approach,¹⁵² our primary analysis will include all randomized participants who complete the baseline survey, independent of early dropout. Participants who are missing abstinence data will be assumed to be smoking. Missing survey data on other outcomes will be imputed using multiple imputation.¹⁵³ For our Aim 1 primary outcome, we will compare the proportion of participants who achieved CO-verified (< 6 ppm) 7-day point-prevalence abstinence at the end of treatment between conditions that were provided NRT versus no NRT using logistic regression. For our Aim 2 primary outcome we will compare the proportion of participants who achieved CO-verified 7-day point-prevalence abstinence at the end of treatment between conditions assigned to quit CCs only versus quit CCs and Ecs simultaneously. For our Aim 3 primary outcome we will compare the conditions assigned to quit CCs only versus quit CCs and Ecs simultaneously on 1) the proportion of participants who report a serious study-related adverse event using a chi-square test and 2) the total number of reported study-related adverse events during the treatment period using a t-test or nonparametric test, depending on the distribution. In addition, we will conduct an exploratory analysis using logistic regression to examine the interaction between the treatment arms (NRT versus no NRT by continue EC versus quit EC) with CO-verified 7-day point-prevalence abstinence as the outcome. We will also examine the effect of EC continuation versus NRT on CC abstinence by comparing Group B (quit CCs and Ecs with NRT) versus Group C (quit CCs and continue Ecs without NRT) using logistic regression. We will conduct a series of sensitivity analyses using 30-day abstinence at the 6-month follow up as the outcome and test condition as a predictor of time to relapse after quit day using Cox proportional hazards regression survival analyses. Finally, we will conduct sensitivity analyses when missing data are treated as missing.

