Additional secondary analyses will explore moderators and intervention effects on relevant smoking outcomes. For example, we will test days of NRT use as a moderator of NRT's effect on abstinence using logistic regression. Similarly, we will test days of EC use as a moderator of the effect of being assigned to continue versus quit Ecs on CC abstinence using logistic regression. We will assess baseline preference for continuing versus quitting Ecs as a moderator of the effect of being assigned to continue versus quit Ecs on CC abstinence using logistic regression. Among participants who fail to quit CCs, we will examine condition as a predictor of change in amount of CC use, self-reported attempts to quit CCs, nicotine dependence, self-efficacy to quit CCs, and motivation to quit CCs. Analyses will be performed using SAS Statistical Software V9.4 (SAS Institute, Cary, NC). Statistical significance will be determined based on p<.05 for all analyses.

Sample size justification. We propose recruiting, consenting, and randomizing a sample of 390 participants. Given the high rate of fraudulent responses in remote studies, we anticipate that we will need to consent 1,030 individuals in order to verify the identification and randomize 390 participants. Based on prior remote tobacco treatment research among young adults,³³ we estimate 80% retention of randomized participants and thus anticipate retaining 312 participants by the end of treatment when we will assess our primary outcome. This proposed sample size is based on having sufficient power for detecting group differences on the primary outcome of 7-day point-prevalence abstinence at the end of treatment (i.e., week 12) for the treatment comparisons in Aims 1 and 2. A sample size of 78 in each of the 4 treatment groups will give over 90% power to detect a difference between NRT and No NRT and 80% to detect a difference between CC+CE and CC only in 7-day point-prevalence abstinence rates, assuming overall rates of 31% in the NRT and 12% in the No NRT group and overall rates of 15% in the CC+CE and 28% in the CC only group with $\alpha=.05$. While we know of no prior trials of NRT for young adults or smoking cessation treatment for dual users, these estimates are based on relevant prior trials of NRT or text messages for smoking cessation.^{37,69,140,154}

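### Aims 1 and 2 are each compared one factor at a time, with no method named for Aim 2; a single model with both randomised factors would be a small, free improvement

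*Combined protocol and SAP*

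**What the plan says.** Section 3.C.3 (Research Design) and Table 1 set out a 2x2 factorial trial: NRT or none, crossed with text messages to continue or to quit ECs.

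Under Statistical Considerations, the Statistical methods paragraph treats the factors one at a time:

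- **Aim 1.** Abstinence is compared "between conditions that were provided NRT versus no NRT using logistic regression". No model terms are listed and the EC factor is not mentioned.
- **Aim 2.** The text reads "For our Aim 2 primary outcome we will compare the proportion of participants" who are abstinent, by EC instruction. No test or model is named and NRT is not mentioned.
- **Covariates.** The only candidates are characteristics found to differ between conditions at baseline.
- **Both factors together.** They meet only in an exploratory logistic regression for the interaction.

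The Sample size justification uses marginal rates: "assuming overall rates of 31% in the NRT and 12% in the No NRT group". For the EC factor it takes 28% where ECs are continued and 15% where both products are quit (the plan labels the latter CC+CE). With "A sample size of 78 in each of the 4 treatment groups" it claims "over 90% power to detect a difference between NRT and No NRT and 80% to detect a difference between CC+CE and CC only". The threshold is given as "Statistical significance will be determined based on p<.05 for all analyses".

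**The concern.** In a factorial trial each randomised factor is a candidate predictor of the outcome for the other factor's test. The planning rates assume that NRT strongly predicts abstinence. An Aim 2 comparison without NRT therefore leaves unused some information that the design creates, and lets any chance difference in NRT share between the EC arms pass into the estimate.

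Aim 2 has the smaller assumed effect and the lower planned power, so what is lost falls there. In addition, Aim 2 has no stated method and neither aim has listed terms, so the primary models are left to be settled at analysis.

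**Working it through.** **Inputs.** Sample size justification: 78 per cell, so 156 against 156 for each factor; NRT 31% against 12%; EC 28% (continue) against 15% (quit); alpha 0.05. Assumptions of this check: two-sided tests, equal cells unless stated, and no interaction on the logit scale.

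**1. The plan's own power.** Two-proportion test, pooled variance under the null:
power = Φ[(|p1 − p2| − 1.96·SE0) / SE1], where SE0 = √(2·p̄(1 − p̄)/156) and SE1 = √((p1(1 − p1) + p2(1 − p2))/156).

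- EC: p̄ = 0.215, SE0 = 0.0465, SE1 = 0.0459. Power = 80.1% (plan: 80%).
- NRT: p̄ = 0.215, SE0 = 0.0465, SE1 = 0.0453. Power = 98.6% (plan: over 90%).

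Both figures reproduce as one-factor comparisons. This supports reading the primary analyses that way, although the plan does not list model terms.

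**2. Cell rates implied by the margins.** Solving a main-effects logit model for the stated margins gives A 39.8%, B 22.2%, C 16.2%, D 7.8%. Check: (39.8 + 22.2)/2 = 31; (16.2 + 7.8)/2 = 12; (39.8 + 16.2)/2 = 28; (22.2 + 7.8)/2 = 15.

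**3. Odds ratios.**

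| Factor | One-factor | Two-factor | Ratio of log odds ratios |
|---|---|---|---|
| NRT | (0.31/0.69)/(0.12/0.88) = 3.29 | 3.40 | 0.974 |
| EC | (0.28/0.72)/(0.15/0.85) = 2.20 | 2.31 | 0.945 |

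The one-factor log odds ratios are 2.6% and 5.5% smaller.

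**4. Power, one-factor against two-factor, 78 per cell.**

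Asymptotic Wald power is Φ(log OR/SE − 1.96):

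- EC: 0.790/0.2865 = 2.758, so 78.8%; with both factors 0.836/0.2950 = 2.833, so 80.9%.
- NRT: 1.192/0.3011 = 3.960, so 97.7%; with both factors 1.225/0.3055 = 4.008, so 98.0%.

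Simulation (10,000 trials):

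- EC: Wald 81.3% against 83.1%; likelihood ratio 82.1% against 83.4%.
- NRT: 98.9% for both models.
- With effects additive on the risk scale instead (cells 37.5/24.5/18.5/5.5%), EC Wald power is 81.2% against 82.9%.

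**5. Type I error** (Wald), when the other factor has its planned effect: one-factor 4.7% (NRT) and 4.0% (EC); two-factor 5.0% and 4.7%. Neither exceeds the nominal level.

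**6. Unequal cells.** The document describes no blocking or stratification. If randomisation were simple (an assumption), Aim 2 likelihood-ratio power at N = 312 would be about 80.5% with one factor and 82.8% with both. The SD of the difference in NRT share between EC arms is √(0.5/156) = 5.7 points at N = 312 and √(0.5/195) = 5.1 points at N = 390.

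Take a 10-point imbalance, just under 2 SD: NRT share 45% in the continue arm and 55% in the quit arm.

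- Continue: 0.45 × 39.8 + 0.55 × 16.2 = 26.8%.
- Quit: 0.55 × 22.2 + 0.45 × 7.8 = 15.7%.
- The unadjusted difference is 11.1 points instead of 13.0, and the odds ratio 1.96 instead of 2.20.

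A model with both factors corrects for this. The opposite imbalance is equally likely, so this is chance error in a single trial, not bias over repeated trials.

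**The case against.** The strongest reply is that nothing is wrong with the tests. The factors are randomised independently, the plan speaks of comparing proportions, and its power rests on overall rates, so the marginal effect is a coherent target and a one-factor comparison estimates it. That stands.

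Three stronger readings are tempting, and the documents do not support them:

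- **That the one-factor odds ratio is biased.** It is not. 2.20 is a marginal and 2.31 a conditional odds ratio; they answer different questions. On the risk-difference scale with equal cells, both approaches give (39.8 + 16.2)/2 − (22.2 + 7.8)/2 = 13 points.
- **That NRT is a known strong predictor being ignored.** The sample-size paragraph says the authors are aware of no earlier NRT trials in young adults and no cessation-treatment trials in dual users. The 31% and 12% are planning assumptions.
- **That Aim 2 has no power to spare.** The 80% is computed at 312. The primary analysis keeps every randomised participant who completes the baseline survey and counts missing abstinence as smoking, so the analysed number can exceed 312. At 195 per level the two-proportion formula gives 88.1%, provided the assumed rates already allow for that counting rule, which the plan does not say.

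It is also fair that the plan never says each model holds only one factor, and that an Aim 2 odds ratio is itself an inference because no model is named. But if two-factor models were intended, that is not written either, and the same wording settles it.

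A last objection is that a main-effects model assumes a common conditional odds ratio while interaction remains an open question. Reporting standardised risk differences largely meets this: with equal cells, the logistic score equations make the standardised difference equal the observed difference in proportions, whether or not there is an interaction.

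**Conclusion.** The point holds as a modest improvement. Neither primary comparison mentions the other randomised factor, and Aim 2 has no named method. Under the plan's assumed rates, one-factor analysis gives up about 1 to 2 points of power for Aim 2 and at most about 0.3 for Aim 1, and leaves chance imbalance between the factors unadjusted. The primary tests remain valid and type I error is not inflated.

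The size depends on the planning rates being roughly right. If NRT has little effect, the Aim 2 gain shrinks towards nothing. It is little changed whether effects are additive on the logit or the risk scale. The larger figure under unequal cells assumes simple randomisation.

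**What to change.** In the Statistical methods paragraph, specify one primary logistic regression for CO-verified 7-day abstinence at end of treatment, with NRT (yes/no) and EC instruction (continue/quit) as main effects. Test Aim 1 and Aim 2 from the two coefficients of that model. Report model-standardised risk differences with 95% CIs, so that the target stays the marginal difference in proportions used for the sample size. Add the product term to the same model for the exploratory interaction test.

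This also supplies the missing Aim 2 method and fixes the treatment terms in advance. In the text, call NRT an assumed predictor, and do not describe a lower one-factor odds ratio as bias.

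Cost: a few sentences, with no extra participants, data or assessments. The sample size need not change, because the present calculation is slightly conservative for the two-factor model under the planned rates.

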3. RESEARCH STRATEGY

3.A. SIGNIFICANCE

3.A.1 Need for smoking cessation treatment for young adults

Young adulthood (i.e., ages 18-29) is a pivotal developmental period when there is high risk of becoming a long-term cigarette smoker^{26,50,51} and thus a crucial need for effective smoking cessation treatment.⁵² Above all, cessation in young adulthood can prevent long-term morbidity and mortality from cigarettes.²²⁻²⁶ Though young adults are more likely to attempt to quit^{27,53,54} they are less likely to succeed²⁷ than older adults. Further, young adults are less likely to use evidence-based treatments when trying to quit²⁸⁻³¹ which may reflect the paucity of acceptable and effective smoking cessation treatments for this age demographic.^{36,39} Thus, there is a need for research to tailor effective smoking cessation treatments for young adults.

As outlined by NCI's Tobacco Control Research Priorities, innovative treatments that adapt to young adults' changing demographics and dual use are needed.⁵² In line with this report, our recent systematic review identified the need for research on pharmacological smoking cessation treatment for young adults.³⁶ Nicotine replacement therapy (NRT) is effective for smoking cessation³⁷ and internationally recognized as a first-line treatment for adults who want to quit smoking cigarettes.^{38,55-58} Use of NRT increases the success of smoking cessation by approximately 50% to 60% in adults.³⁷ Though self-selected use of NRT is associated with increased smoking cessation among young adults,⁵⁹ we know of no RCTs of NRT using a sample of young adults.^{36,39} Research on NRT specific to young adult smokers is particularly important given that they are more likely to use additional tobacco products⁶⁰ and less likely to use tobacco daily than older adults,⁶¹ which could influence the effectiveness of NRT (e.g.⁶²). Further, the relative ease of obtaining NRT in the United States (i.e., NRT is sold over-the-counter) may make it more appealing than other prescription medications given that young adults are less likely than older adults to engage in formal treatment.²⁸⁻³¹ Thus, there is a need for research on NRT for smoking cessation among young adults. This need will be directly addressed by Aim 1 of the proposed RCT.

Though NRT is sometimes delivered by healthcare providers in conjunction with counseling,⁶³ text-message based

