Assessments. All assessments will be remote and accessible by smartphone, tablet, or computer. After confirming eligibility and consenting to participate, participants will be randomly assigned to one of the four study groups (Table 1) and study personnel will mail a welcome package including study information, a CoVita iCO personal smokerlyzer device, and NRT (for groups A and B only). Upon receipt of the welcome package, participants will complete a brief baseline survey on the internet (Table 2) and will be encouraged but not required to submit a baseline breath CO sample using the CoVita iCO device and iCOquit mobile application which is compatible with Mac iOS and Android operating systems for smartphones and tablets. We will not ask participants to return their personal CoVita iCO Smokerlyzer. All participants will be free to keep their personal CoVita iCO Smokerlyzer after the conclusion of their participation.

Table 2. Schedule of assessments

	Baseline	Daily 1 wk pre- and 1 wk post-quit	Weekly surveys and End of Tx	6-Month follow-up
Human subjects protocol form 1/25/2022				

Individual-level factors				
Socio-demographic information	x			
Tobacco use history & breath CO	x			
Motivation rulers for CC & EC cessation ¹²⁵	x		x ^a	x ^a
CC and EC dependence and demand				
CC Strong dependence questionnaire	x		x ^a	x ^a
EC Strong dependence questionnaire	x		x ^a	x ^a
Cigarette & e-Cigarette Purchase Tasks ¹²⁸	x		x ^a	x ^a
Minnesota Nicotine Withdrawal Scale ¹³¹	x		x	x
Intervention engagement & adverse effects				
Preference for quitting CCs only versus CCs + ECs simultaneously	x			
Frequency of EC use (groups A & C) or EC abstinence (groups B & D)		x	x	x
NRT use and perceived helpfulness (groups A & B)		x	x	
Responses to text messages and perceived helpfulness		x	x	
Study-related adverse effects		x	x	x
Outcomes				
Primary: CO-verified 7-day point prevalence CC abstinence			x	x
Secondary:				
CO-verified 30-day CC abstinence			x	x
Self-reported attempts to quit CCs		x	x	x
Cigarettes per day	x	x	x ^a	x ^a
Time to first CC after waking ¹³² and CC addiction ladder	x	x	x ^a	x ^a

^aAssessed only among participants who relapsed or failed to quit CCs. CC=Combustible cigarettes; EC=Electronic cigarette; NRT=Nicotine replacement therapy; Tx=Treatment.

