All participants will complete brief daily surveys for two weeks: one week pre- and one week post-quit date.. Participants will receive a daily text and/or email containing a link for the daily survey and will be able to complete the survey via internet on a smartphone, tablet or computer. Prior research from our group indicates 2 weeks of daily surveys is feasible with good retention (95%).¹³³ Participants will report CC smoking, EC use, NRT use (groups A and B only), text message utilization, nicotine dependence, quit attempts, and adverse events on daily surveys (Table 2). At the conclusion of the 12-week treatment period, participants will complete an end of treatment survey to report CC smoking or EC use and withdrawal symptoms. Those still smoking will also report motivation to quit, nicotine dependence, and self-efficacy to quit. In addition, participants will be encouraged but not required to submit another breath CO sample using their CoVita iCO device. The primary outcome for this RCT is CO confirmed 7-day point-prevalence abstinence from CCs at the end of treatment (i.e., at the 3-month follow-up). Per the Society for Research on Nicotine and Tobacco (SRNT) report on biochemical verification,¹³⁴ we will use CO of < 6 parts per million (ppm) as the cutoff for confirming CC abstinence. We will not contact participants for the 12 weeks following the treatment period. All participants will then complete a 6-month follow-up survey (i.e., 24 weeks after the baseline assessment) to report any CC smoking or EC use and withdrawal symptoms. Those who relapsed or continued to smoke CCs will also report motivation to quit, nicotine dependence, and self-efficacy to quit. In addition, all participants will be encouraged but not required to submit a final breath CO sample using their CoVita iCO device.

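### Two exploratory analyses do not support the reading given to them: NRT days, collected only in groups A and B, cannot moderate NRT's effect, and comparisons among non-quitters are not randomised

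*Combined protocol and SAP*

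**What the plan says.** The paragraph on additional secondary analyses under Statistical Considerations says these will explore moderators and intervention effects. Three items matter here.

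- **NRT days.** The plan states "we will test days of NRT use as a moderator" of NRT's effect on abstinence, by logistic regression. Table 2 lists the item as "NRT use and perceived helpfulness (groups A & B"), and the Assessments text agrees: "Participants will report CC smoking, EC use, NRT use (groups A and B only"). Eligibility excludes current NRT users, so this variable arises only after randomisation.
- **Failure-only comparisons.** "Among participants who fail to quit CCs, we will examine condition as a predictor of change in amount of CC use", and likewise quit attempts, dependence, self-efficacy and motivation. Footnote a of Table 2 restricts several of these measures, including follow-up cigarettes per day, to people who relapsed or failed to quit. The quit-attempts row does not carry that footnote.
- **EC days.** Days of EC use is named as a moderator of the EC assignment, with no time window.

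Failure to quit is not defined. On the survey, "Those still smoking will also report motivation to quit, nicotine dependence, and self-efficacy to quit", which points to reported smoking. The primary outcome needs CO confirmation, but "participants will be encouraged but not required to submit another breath CO sample", and "Participants who are missing abstinence data will be assumed to be smoking". The same section applies a 0.05 significance level to every analysis.

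**The concern.** A moderator test asks whether the NRT versus no-NRT contrast changes with the moderator, so the moderator must be observed on both sides of that contrast. NRT days is not. Nor is zero a verified value in C and D, since section 3.A.1 notes that "NRT is sold over-the-counter" and those groups are not asked. What can be estimated is how abstinence varies with days of use inside A and B. That is a non-randomised association and is open to reverse causation, because people who relapse may stop using NRT.

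Failure to quit is settled after randomisation, and the treatments are expected to change it. If NRT helps the easier quitters to stop, those left smoking in the NRT arms are a harder group than those left in the other arms. They can then differ on dependence or motivation with no treatment effect on either.

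The stake is interpretation. A significant NRT-days result could be reported as effect modification, and a significant failure-only result as an intervention effect among continuing smokers. The design supports neither.

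**Working it through.** **The plan's own figure.** Inputs from Sample size justification: 78 per cell, so n = 156 per side of each factor; 31% vs 12% (NRT) and 28% vs 15% (EC); alpha 0.05, taken as two-sided. With pooled proportion p̄ = 0.215 for both factors,

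power = Φ{ [|p1 − p2| − 1.96·√(2p̄(1−p̄)/n)] / √(p1(1−p1)/n + p2(1−p2)/n) }.

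- NRT: (0.190 − 0.0912)/0.0453 = 2.18, power 98.6% (stated: over 90%).
- EC: (0.130 − 0.0912)/0.0459 = 0.85, power 80.1% (stated: 80%).

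The rates and sample size are therefore read as the plan intends. The plan gives no figures for the analyses at issue.

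**NRT days.** The usual moderator model has four columns: intercept, NRT, days, NRT × days.

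- Days = 0 in C and D: NRT × days equals days in every row. Rank 3 of 4, so the interaction is aliased with days.
- Days missing in C and D: only A and B remain, where NRT = 1 throughout. NRT equals the intercept and NRT × days equals days. Rank 2 of 4, so the NRT effect is lost as well.

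Either way, the only slope on days comes from within A and B.

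**Who is in the failure-only set.** Taking failure as the complement of the primary outcome, at 156 per side:

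| Factor | Failure fractions | Failures |
|---|---|---|
| NRT vs no NRT | 1 − 0.31 = 69% vs 1 − 0.12 = 88% | 108 vs 137 |
| CC only vs CC and EC | 1 − 0.28 = 72% vs 1 − 0.15 = 85% | 112 vs 133 |

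**One illustration of the consequence.** Assumptions, none fixed by the documents: a latent quit difficulty Z ~ N(0,1); the easiest fraction p quit; the outcome Y has correlation ρ with Z, unit variance and no treatment effect; a Welch test is done among failures.

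- Mean of Z among failures: m(p) = φ(z_p)/(1 − p), with z_p = Φ⁻¹(p).
- Variance of Z among failures: v(p) = 1 + z_p·m(p) − m(p)².
- Spurious shift in Y: ρ·[m(p1) − m(p2)].
- Variance of Y among failures: ρ²·v(p) + 1 − ρ².

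NRT: m(0.31) = 0.511 and m(0.12) = 0.227, difference 0.284. EC: m(0.28) = 0.468 and m(0.15) = 0.274, difference 0.193.

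At ρ = 0.5 the NRT shift is 0.5 × 0.284 = 0.142 SD, with standard error √(0.871/107.6 + 0.920/137.3) = 0.122, ratio 1.17. The EC shift is 0.097 SD, with standard error 0.121, ratio 0.80.

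| ρ | NRT: shift (SD), rejection | EC: shift (SD), rejection |
|---|---|---|
| 0.1 | 0.028, 5.6% | 0.019, 5.3% |
| 0.2 | 0.057, 7.3% | 0.039, 6.1% |
| 0.3 | 0.085, 10.3% | 0.058, 7.4% |
| 0.5 | 0.142, about 21% | 0.097, 12.5% |

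Without the restriction to failures the shift is zero in this model and the test keeps its 5% level.

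**EC days.** No arithmetic applies. A count taken before randomisation could serve as a moderator. A count taken on treatment is what the EC assignment is meant to change, so it could not.

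**The case against.** The best reply is that little hangs on this. The analyses are introduced as additional and exploratory, the NRT-days test is offered as an example, and Aims 1 to 3 and the sample size do not depend on them. With zero coding, a model containing arm and days does fit, so the first part could be called a matter of labelling. The limited consequence stands, and it is why the point goes no further than these analyses. It does not rescue the stated reading: the fitted slope is still not a moderator effect, and the plan attaches no associational caveat.

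It is also fair that the rejection rates are not evidence from the plan. The correlation and the latent model are assumed, and at ρ = 0.1 to 0.2 the inflation is modest. Only the failure fractions follow from the documents, and they rest on rates assumed for the primary outcome. A reader might infer that the same gaps hold for self-reported smoking or for sets that count dropouts as smokers. The plan gives no rates for those definitions.

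On EC days, two stronger inferences are tempting. One is that different EC data are collected by arm, because Table 2 words the row as frequency for A and C and abstinence for B and D. The Assessments text has participants report EC use without restriction by group and limits only NRT use to A and B, so the label does not show this. The other is that no baseline EC measure exists, because that row has no baseline mark. Table 2 marks tobacco use history at baseline, and the adverse-event rules compare EC use with baseline, so some baseline measure is implied.

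**Conclusion.** The point holds for two exploratory analyses. That NRT days cannot be tested as a moderator is algebra and needs no assumption beyond the usual product-term model. That the failure-only comparison is not randomised follows from conditioning on a post-randomisation status which the plan's own rates expect to differ: 69% vs 88% and 72% vs 85%. How much a test would be distorted is not known. The illustrated 5.6% to 21% and 5.3% to 12.5% depend on the assumed correlation and on failure being the complement of the primary outcome.

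A reader might take this to weaken the primary abstinence comparisons. It does not: those use all randomised participants who complete the baseline survey and do not condition on quitting. The EC-days item is a minor omission, an unstated window, and no more.

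**What to change.** 1. **NRT days.** Drop it as a moderator. Report it as a non-randomised dose-response association within A and B.
2. **Failure-only outcomes.** Compare quit attempts and end-of-treatment cigarettes per day (0 if abstinent) by condition in the analysis set already defined under Statistical methods, namely all randomised participants who complete the baseline survey. Use the planned multiple imputation for missing values, and state how it fits with counting missing abstinence as smoking; otherwise someone classed as smoking could receive an imputed value of zero. If change in cigarettes per day is reported, note that the baseline survey follows randomisation and the mailed package, or use a screener value if one is stored.
3. **Labels.** Define failure to quit. Present the failure-only results (dependence, self-efficacy, motivation) as descriptive, not as intervention effects.
4. **EC days (minor).** State the window. If a moderator is meant, use a pre-randomisation count, such as the past-30-day screening item if the number of days is stored and not only the eligibility threshold. Report on-treatment EC days descriptively.

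Cost: analysis-plan wording, plus a check of what the screener stores. No new data are needed for items 1 to 3: quit attempts are not restricted to failures in Table 2, and an abstainer's current cigarettes per day is zero. The small downside is that the all-participant comparisons partly track the primary outcome and answer a different question from the one about continuing smokers, which remains as description.
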